Study Design	
The study is a two-arm, open label, randomized trial. All groups will receive standard intensive diabetes treatment with insulin and dietary management. There will be four groups of participants in this study
 
 
 Group	Subject population	
 
 I	Fourteen (14) adults (18-65 years) of established T1D of more than 6 months duration (>180 days) and up to 10 years	
 
 II	Fourteen (14) adults (18-65 years) of new-onset T1D diagnosed within last 6 months (\leq 180 days)	
 
 III	Fourteen (14) children (6-17 years) of established T1D of more than 6 months duration (>180 days) and up to 10 years	
 
 IV	Fourteen (14) children (6-17 years) of new-onset T1D diagnosed within last 6 months (\leq 180 days)	
 
 
Participants in each group will be randomly assigned in a 1:1 ratio to receive either one year of high dose Omega-3 fatty acids and Vitamin D combination (Arm A) or Vitamin D alone (Arm B). Both arms will receive Vitamin D supplementation.
 
Table 1. This table represents supplements used in the study, their doses, routes of administrations and description of two arms
 
 
 Drugs with route of administration	Dose	Arm A	Arm B	
 
 Ultra-refined omega-3 EPA/DHA concentrate in Liquid or	 Based on the body weight of the participant Initial Dose: 	Three times daily orally		
 
			Group	Subject population	I	Fourteen (14) adults (18-65 years) of established T1D of more than 6 months duration (>180 days) and up to 10 years	II	Fourteen (14) adults (18-65 years) of new-onset T1D diagnosed within last 6 months (\leq 180 days)	III	Fourteen (14) children (6-17 years) of established T1D of more than 6 months duration (>180 days) and up to 10 years	IV	Fourteen (14) children (6-17 years) of new-onset T1D diagnosed within last 6 months (\leq 180 days)	Drugs with route of administration	Dose	Arm A	Arm B	Ultra-refined omega-3 EPA/DHA concentrate in Liquid or	Based on the body weight of the participant Initial Dose:	Three times daily orally	
Group	Subject population																				
I	Fourteen (14) adults (18-65 years) of established T1D of more than 6 months duration (>180 days) and up to 10 years																				

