II	Fourteen (14) adults (18-65 years) of new-onset T1D diagnosed within last 6 months (\leq 180 days)																				
III	Fourteen (14) children (6-17 years) of established T1D of more than 6 months duration (>180 days) and up to 10 years																				
IV	Fourteen (14) children (6-17 years) of new-onset T1D diagnosed within last 6 months (\leq 180 days)																				
Drugs with route of administration	Dose	Arm A	Arm B																		
Ultra-refined omega-3 EPA/DHA concentrate in Liquid or	Based on the body weight of the participant Initial Dose:	Three times daily orally																			

	
Capsule formulations (ZoneLabs® OmegaRx®2 Fish Oil – Liquid; containing 3375 mg EPA+DHA [2250 mg EPA and 1125 mg DHA] in 5 mL
 
Of note, each 1 mL of OmegaRx®2 contains 675 mg of EPA+DHA.
	
150 mg of EPA+DHA per Kg body weight.
 
Maintaince Dose: Dose will be adjusted to maintain a target AA/EPA ratio of 1.5-3.0. AA/EPA ratios will be monitored monthly until achieving target levels and as per protocol or as clinically indicated thereafter.
 
It is 150 mg of combined EPA and DHA per kg body weight to be given either as a single or divided into smaller doses through the day.
		
	
Vitamin-D 25OH (Cholecalciferol)
	
Based on the Vitamin D level and age of the participant
 
For levels 30 -39 ng/ml:
 
Age ≤10 years give 500 IU daily
 
Age >10 years give 1000 IU daily
 
For levels 20 – 29 ng/ml
 
50,000 IU weekly for 2 months and then:
 
Age ≤10 years give 1000 IU daily
 
Age >10 years give 2000 IU daily
 
For levels < 20 ng/ml
	
Daily orally
	
Daily orally

		
50,000 IU weekly for 6 months and then:
 
Age ≤10 years, give 1000 IU daily
 
Age >10 years, give 2000 IU daily
 
Dose will be adjusted and monitored every four months until achieving target levels and as clinically indicated thereafter.
		
Treatment Description	Subjects will be randomized to one of the two arms. The treatment arm A includes Omega-3 Fatty Acids and Vitamin D. The subjects randomized in Arm B (control group) will receive only Vitamin D supplement. The treatment assignment will be conducted in a open label fashion.			

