4.6. Description of Treatment Groups

This open label protocol will enroll a total of 56 participants who will be randomly assigned (1:1) to the following groups:

- 28 participants will be assigned to receive Omega-3 Fatty Acids and Vitamin D combination following randomization, and then will be followed for an additional year.
- 28 participants will receive only Vitamin D.

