9.2. Endpoints/Outcomes

Primary endpoint:

- Stimulated (90 minute sample of a MMTT) C-peptide at the 1 year visit greater or equal to baseline level.

Secondary Objective(s)

- Stimulated C-peptide area under the curve during a 4-hour MMTT greater or equal to baseline level, at the 1 year visit.
- Reduction in HbA1c at the one year visit compared to baseline.
- Reduction in insulin requirement at the 1 year visit compared to baseline.
- Incidence of adverse events (AE) comparable to general diabetes population.

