9.6. Statistical Hypotheses

Primary hypothesis:

- Null: Patients receiving combination supplement therapy and patients in the Vitamin-D alone group have comparable proportions with maintained or increased C-peptide production, assessed by the measurement of the stimulated 90-minute C-peptide at one year of follow up.
- Alternative: Patients receiving combination therapy have higher proportions with maintained or increased C-peptide production, assessed by the measurement of the stimulated 90-minute C-peptide as compared to the proportion of patients with maintained or increased C-Peptide in the vitamin D alone group at one year of follow up.

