9.7. Sample Size Considerations

Metabolic primary outcome

Sample size considerations correspond to the primary hypothesis which is that the proportion of patients with maintained or increased 90-min C-peptide at 12 months compared to baseline value is greater in the combination therapy group than in the vitamin D alone group. Standard power calculations for two sample tests of proportions indicate that 12 subjects in each group are needed to achieve 80% power to detect differences between less than 5% in the vitamin D alone group and at least 50% in the combination therapy group. Allowing for 10% dropout/attrition, sample size considerations include an allowance for 10% of the subjects to have missing data (one-year MMTT was not done or subject withdrew prior to the one-year assessment).

Primary endpoints should be available for all enrolled subjects. An exception will be if a death occurs or if the subject withdraws consent to be followed, although we expect this to be very limited. We also have included consideration for attrition in our design. Should there be any missing data, missing data will be assessed for mechanism of missingness and to see if missing at random assumptions are valid. If necessary, appropriate imputation strategies can be applied for sensitivity analysis. We will explore the data to assess if missingness at a given time point is related to observed data at the previous time point. If we find that, conditional on treatment group, observed values strongly predict subsequent values where observed, but are not related to missingness at subsequent time points, we may regard the missing data as a random sample of previously observed data.

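### The safety objective is benchmarked against an undefined outside population, and no final adverse-event analysis by randomised arm is specified

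*Combined protocol and SAP*

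**What the plan says.** Sections 1.1, 4.2.2 and 9.2 list the same secondary safety objective: "Incidence of adverse events (AE) comparable to general diabetes population". None of them attaches a time point, a unit of incidence, a data source, a reference rate or a margin. They also do not say whether the incidence is taken per arm or over both arms together.

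The trial is randomised. Section 1.1 states that "Participants in each group will be randomly assigned in a 1:1 ratio" and that "The subjects randomized in Arm B (control group) will receive only Vitamin D supplement". Section 4.6 gives the numbers: "28 participants will be assigned to receive Omega-3 Fatty Acids and Vitamin D combination following randomization", and "28 participants will receive only Vitamin D".

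Safety is also addressed elsewhere:
- Section 4.1 says safety is judged on the AE profile and gives a horizon of one year on treatment plus one year afterwards.
- Section 7.1.6 has the DSMB review AEs by treatment group about every three to six months.
- Section 9.5 includes AEs in the descriptive interim summaries.
- Section 9.5.2 compares the arms with Fisher's exact test at 0.05, at any time, as a reason to consider stopping.
- Section 9.4.1 promises analyses for every trial objective. Sections 9.4.2 to 9.4.4 then cover the C-peptide endpoint and baseline characteristics only.

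**The concern.** The title presents this as a safety and feasibility trial, and it enrols children from age 6. Its only worded safety objective points to a comparator that the plan never defines. The phrase "comparable to general diabetes population" is not limited to type 1 diabetes, to an age range or to a disease duration.

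The trial's own rules also work against a like-for-like comparison:
- Participants must have residual C-peptide and must pass 24 numbered exclusions (4.4.1, 4.4.2).
- They receive intensive diabetes management (5.3, 6.12).
- They are questioned about events (7.1.1, 8.1).
- The AE case report is tied to Grade 2 or above (7.1.6), and hyperglycaemia counts only if it leads to admission (7.1.1.1).

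Some of these raise the observed rate and some lower it, so the net bias against an outside figure is unknown. Almost any result could be described as meeting the objective. What is at stake is a reassuring safety statement in the final report with no analysis behind it.

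**Working it through.** **1. The plan's own figures.** Section 9.7 says "12 subjects in each group are needed to achieve 80% power to detect differences between less than 5% in the vitamin D alone group". The rate assumed for combination therapy is 50% or more. No alpha or sidedness is stated; at 0.05, 12 per group reproduces with the pooled one-sided formula (12) or the unpooled two-sided formula (12), but the pooled two-sided formula gives 15. This calculation concerns C-peptide response. Nothing was sized for AEs.

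The AE examples in section 9.5.2 reproduce with Fisher's exact test:
- 5/6 versus 0/3: C(6,5)·C(3,0)/C(9,5) = 6/126 = 0.048.
- 9/10 versus 1/5: [C(10,9)·C(5,1) + C(10,10)·C(5,0)]/C(15,10) = (50 + 1)/3003 = 0.017.

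Both are below 0.05, as the plan says, so a between-arm AE comparison is workable and already in use for monitoring.

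**2. The external comparison.** It needs a reference rate and a margin. The documents give neither, so there is nothing to calculate. Even if an outside rate were known without error, the exact (Clopper-Pearson) 95% intervals for 28 participants would be wide:
- 3/28: 2.3% to 28.2%
- 7/28: 10.7% to 44.9%
- 14/28: 30.6% to 69.4%

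Pooling both arms, 14/56 gives 14.4% to 38.4%. With no events in 28, the upper limit is 1 − 0.025^(1/28) = 12.3%.

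**3. The randomised comparison.** The inputs are 28 per arm (section 4.6), or 25 after the 10% attrition in section 9.7 (28 × 0.90 = 25.2). The AE rate p is an assumption, taken as 10%, 25% and 50% and equal in both arms. The half-width is 1.96·√[2p(1−p)/n].

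| Assumed rate | Half-width, 28 per arm | Half-width, 25 per arm | Arm A rate detectable, 28 per arm |
|---|---|---|---|
| 10% | ±15.7 points | ±16.6 | 42.2% |
| 25% | ±22.7 points | ±24.0 | 61.4% |
| 50% | ±26.2 points | ±27.7 | 84.5% |

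For example, at 10% with 28 per arm: 1.96·√(0.18/28) = 0.157. The last column takes the assumed rate as the Arm B rate and uses 80% power, two-sided 0.05 and the pooled normal approximation.

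**4. What a claim of comparability would need.** Assume a 10-point margin (also not in the documents), one-sided 0.025 and 80% power. Then n per arm = (1.96 + 0.8416)²·2p(1−p)/0.10²:
- 10%: 7.849 × 0.18/0.01, or 142
- 25%: 7.849 × 0.375/0.01, or 295
- 50%: 7.849 × 0.50/0.01, or 393

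The trial has 28.

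**The case against.** The strongest reply is that safety is not left to this one line. Section 4.1 supplies a two-year horizon, and section 8.1 says when AE collection starts and ends. The DSMB sees AEs by arm, and section 9.5.2 tests them between arms. This stands. A reader might infer from the objective that the trial has no safety time frame or plans no between-arm AE comparison; the documents contradict both. The gap is that the objective does not use that comparison and section 9.4 does not carry it into a final analysis.

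A reader might also infer that an outside comparison is impossible. That goes too far. A descriptive one could be made if a source were named; it is only the comparison as planned that cannot be carried out.

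Omitting Arm B from the objective is not a fault in itself. The primary objective omits it too, and section 9.4.2 supplies the contrast. The AE objective differs because it names another comparator and no analysis section corrects it.

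Arm B also does not answer every safety question. Both arms take vitamin D, so A versus B says nothing about the safety of vitamin D, which the title also covers. The trial is open label, so AE reporting may differ by arm. Both points stand and belong in the text.

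Finally, the wide intervals apply to the between-arm comparison as much as to the outside one. That is correct: they do not measure the wording defect. They show why the report should give estimates with intervals and make no claim of comparability against either reference.

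**Conclusion.** The point holds as a defect in the objective and in the final analysis. The benchmark has no source, rate, margin or test, and section 9.4 specifies no final AE analysis despite the commitment in 9.4.1. It is not a failure of participant-level monitoring, which has its own between-arm rule, and it does not touch the primary endpoint.

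The size of any error against the outside population cannot be computed, because its rate is not given. What the randomised arms can deliver is a difference known to within about ±16 to ±26 points, assuming AE rates of 10% to 50%, 28 evaluable per arm and a normal approximation. With no events in an arm, a true rate up to 12.3% remains possible. These figures support an estimate with its interval and do not support the word *comparable*.

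**What to change.** **Objective (1.1, 4.2.2, 9.2).** Restate it as AE and SAE incidence by arm through months 12 and 24. Remove *comparable*. Drop the general-population comparison, or keep it only as descriptive context with a named source.

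**Final analysis (add to 9.4).**
- (a) The proportion with at least one AE, and with at least one SAE, in each arm with exact 95% intervals.
- (b) The Arm A minus Arm B risk difference with a 95% interval, naming the interval method in advance.
- (c) Events per person-year by arm, with a rate ratio or rate difference and a 95% interval. A risk difference is not the right summary for person-year rates.

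**Interpretation.** State that A versus B isolates omega-3, that the safety of vitamin D rests on the within-arm rates, and that AE reporting is open label.

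**Numerator.** Reconcile the capture rules first. Section 7.1.1.1 puts Level 2 and Level 3 hypoglycaemia on the case report form as AEs, while 7.1.4 calls only Level 3 reportable. Section 7.1.5 puts all AEs on the form on a three-point scale, while 7.1.6 requires the AE case report from Grade 2 upwards. Until one rule applies, the proportion with at least one AE has no fixed meaning.

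**Cost.** Wording in three places, one added analysis, and the reconciliation in section 7. Appendix A already schedules AE assessment from month 4 to month 24, so no new visits or participants are needed. The downside is small: no claim of comparability can be made.

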9.3. Measures to Minimize Bias

Participants who completed the screening visit and are determined to be eligible for study participation will undergo randomization. Participants will be randomized by the study PI at the clinical site. The participants will be informed regarding the intervention assignment.

9.4. Analysis Plan

The details of the analyses will be provided in the statistical analysis plan (SAP) below.

9.4.1. Analysis Populations

Analyses of study data will be conducted to address all objectives of the trial and other interrelationships among data elements of interest to the investigators and of relevance to the objectives of the study. Primary analysis of treatment effect will be conducted under the intention-to-treat principle of eligible patients whereby outcome data from all eligible patients will be included regardless of treatment compliance.

9.4.2. Primary Analysis of Primary Endpoint(s)/Outcome(s)

The metabolic primary outcome is the 90-minute stimulated C-peptide following MMTT, conducted at the 1 year visit. The primary statistical hypothesis to be assessed is that the proportion of patients with maintained or increased level of 90-minute at 12 months as compared to baseline will be greater in subjects receiving combination therapy than for subjects receiving vitamin D alone.

The analysis of the primary outcome will initially involve a two sample test of proportions comparing the proportion of patients in the combination therapy group maintaining or increasing 90-C-peptide with respect to baseline with the proportion of vitamin D alone treated subjects with 90-minute C-peptide that is maintained or increased from baseline value. A covariate-adjusted analysis will additionally be performed by way of a logistic regression model, with a categorical index of treatment group adjusted for baseline age and time since diagnosis; this can provide us with adjustment for potential confounding of these factors and/or provide increased efficiency and precision by including these potentially significant explanatory variables.

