5.2. Randomization

Individuals complying with all inclusion and exclusion criteria and consenting to study participation will be randomized at the clinical site. A blinded statistician will create color and number coded envelopes using a stratified blocked randomization (new diagnosis vs established, child vs adult). Each envelope will contain a card with the corresponding treatment group assignment. Envelopes will be kept in a file cabinet in a secured room at the Diabetes Research Institute. The study PI will perform the randomization of all newly enrolled subjects in a 1:1 ratio to each of the two arms by selecting the corresponding color and number coded envelope to ensure these factors are equally distributed across the two arms of the intervention.

For each subject, the Subject Identificaton Number (SIN), treatment and participant's name will be entered into the study log.

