9.4.4. Descriptive Analyses

In addition to the detailed statistical analysis described above, descriptive analysis will include reporting and comparison baseline characteristics of the study subjects to evaluate whether any substantial differences exist between the vitamin D alone and combination treatment groups for key variables such as age, gender, BMI, HbA1c, baseline C-peptide, insulin requirements and other variables such as concomitant use of other medications to determine any potential bias. These will involve standard two sample comparisons such as T-tests for continuous variables (possibly transformed when necessary to preserve distributional assumptions) and Chi-square or Fisher's exact tests for categorical variables. As described earlier, potentially confounding factors arising from imbalance will be included into more formal statistical models of the investigation.

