APPENDIX A: Schedule of Events (SOE)

Visit number	0	1	2	3	4	5 F1	6 F2	7 F3
Days of the trial ¹	-1	1	120	240	360	480	600	720
Months	1	1	4	8	12	16	20	24
Informed Consent	X							
Medical History	X		X	X	X	X	X	X
Physical Exam ²	X		X	X	X	X	X	X
CBC with differential	X	X	X	X	X			
Prothrombin time (PT/PT-INR)	X		X	X	X	X	X	X
Chemistries	X		X	X	X			
Pregnancy test (blood sample) ⁵	X		X	X	X			
Serum for islet autoantibodies	X		X	X	X	X	X	X
Serology	X							
Mechanistic assessments ³		X	X	X	X	X	X	X
Hemoglobin A1c	X		X	X	X	X	X	X
Stimulated C-peptide at 90 min	X				X			X
MMTT 4 hour	X				X			X
Randomization			X					
Diabetes Assessments (insulin adjustment and Hypoglycemia awareness)	X	X	X	X	X	X	X	X
Clarke Score	X				X			X
Dispensing or Administration of Study Drug		X ⁶	X	X				
• Omega-3 Fatty Acids + Vitamin-D OR • Vitamin-D								
Vitamin D levels ⁴	X		X	X	X	X	X	X
AA/EPA Ratio ⁷	X		X	X	X	X	X	X
Counting of Returned Study Drug			X	X	X			
Subject 7-day blood sugar record and hypoglycemia log	X		X	X	X	X	X	X
Concomitant Medication Review	X	X	X	X	X			
Adverse Events Assessment			X	X	X	X	X	X

1. Screening Visit: Screening MMTT must be at least 3 weeks after diagnosis and preferably within one month (37 days) of randomization for recent onset T1D. For established T1D, screening must take place after 180 days of diagnosis.
2. Physical Exam: Routine exam at screening and quarterly.

3. Mechanistic Assessments: includes samples for RNA, plasma, serum, DNA, measures of B and T cell number/function and cytokine profiles. The schedule for these assessments may vary as appropriate. At no time will the blood draw volume exceed what is allowable according to the subject's body weight.
4. Vitamin D levels will be monitored every 4 months or more frequently at the discretion of the investigator in order to adjust dose to achieve target levels.
5. Pregnancy testing will be conducted in females in reproductive age at 4, 8,12 and 16 months study visit.
6. Study drug(s) will be administered within 48hr from baseline visit (visit 1).
7. Dose will be adjusted to maintain a target AA/EPA ratio of 1.5-3.0. AA/EPA ratios will be monitored monthly until achieving target levels and as per protocol or as clinically indicated thereafter.

F1-F3. Follow-Up after 12 Months: Visits will be conducted approximately every 4 months (16, 20, and 24 months).

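### The primary test leaves out the randomisation strata, and the added logistic model names no test or sparse-data method and admits baseline C-peptide only after an imbalance check

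*Combined protocol and SAP*

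**What the plan says.** Section 1.1 describes four groups of 14, adults and children with new-onset or established disease: "Participants in each group will be randomly assigned in a 1:1 ratio". Section 5.2 calls for "stratified blocked randomization (new diagnosis vs established, child vs adult".

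Section 9.4.2 then sets the primary analysis: "The analysis of the primary outcome will initially involve a two sample test of proportions comparing the proportion of patients". No stratification is mentioned. A logistic model is added, "with a categorical index of treatment group adjusted for baseline age and time since diagnosis", partly to "provide increased efficiency and precision by including these potentially significant explanatory variables". The section does not say whether that model is read by a Wald, likelihood-ratio or score test. It gives no method for sparse data. Fisher's exact test is named only for baseline tables (9.4.4) and adverse events (9.5.2).

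Section 9.4.4 lists baseline C-peptide among the variables to be compared between arms and says that "potentially confounding factors arising from imbalance will be included into more formal statistical models of the investigation". Appendix A has a row "Stimulated C-peptide at 90 min" that is marked at screening and at months 12 and 24.

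Section 9.7 sizes the trial at 12 per group for 80% power to "detect differences between less than 5% in the vitamin D alone group and at least 50% in the combination therapy group", with a 10% allowance for missing data. Section 9.5.3 intends an effect estimate with a 95% interval. Neither alpha nor sidedness is stated for the primary test. The alternative in 9.6 is directional, and 0.05 appears only in the safety rule of 9.5.2.

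**The concern.** There are three gaps in one short section.

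- **Strata.** Stratified randomisation balances the arms on factors expected to matter. A test that then ignores those factors uses too large a variance if they do matter, so it is conservative and loses power.
- **Sparse data.** The plan expects almost no responders on vitamin D alone. If there are none, the maximum-likelihood log odds ratio has no finite value, and the usual readings of the logistic model can disagree completely on the same data. An analyst would choose between them after seeing the outcome.
- **Baseline C-peptide.** The endpoint compares the 12-month value with baseline, so measurement error and regression to the mean make baseline a likely predictor whether or not the arms are balanced. Admitting it only on observed imbalance makes the model data-dependent and may forgo the precision that 9.4.2 says it wants.

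**Working it through.** **Inputs.** From the documents: 56 participants, 1:1 in four strata, so 7 per arm per stratum and 28 per arm; 10% missing, so 28 × 0.9 = 25.2, about 25 evaluable; response below 5% against at least 50%. Assumed: two-sided 0.05, responder rates by stratum, and age and duration uniform within strata.

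**The plan's own figure.** The pooled formula is n = [z_a·√(2p̄(1−p̄)) + z_b·√(p1(1−p1)+p2(1−p2))]² / (p2−p1)², with p̄ = 0.275.
- One-sided 0.05: (1.645 × 0.6315 + 0.8416 × 0.5454)² / 0.2025 = 11.1, so 12. This reproduces the stated figure.
- Two-sided: 14.2, so 15 (unpooled 11.5, so 12).
- 12/0.9 = 13.3, so 14. That is the size of one stratum group, while each arm holds 28, so power at the design rates is ample.

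**Empty vitamin D arm.** P(no responders) = (1−p)^n.
- p = 5%: 0.95^28 = 0.238 and 0.95^25 = 0.277. The plan says below 5%, so these are minimums.
- p = 3%: 0.97^25 = 0.467.
- p = 2%: 0.98^25 = 0.603.

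**One such data set, 0/28 against 14/28.** The pooled z statistic is 0.5 / √(0.25 × 0.75 × 2/28) = 4.32, so the primary test gives a clear answer. In a logistic fit with treatment alone, the log odds ratio diverges (the fit stops at 23.6 with a standard error near 15,000). The Wald p-value is 0.999 and the likelihood-ratio p-value is 9 × 10⁻⁷.

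**Adjusted model, simulated** (10,000 trials per power setting, 5,000 per null, each participant missing with probability 10%). Wald and likelihood ratio use arm, age and duration. Firth uses arm, stratum factors and a baseline covariate.

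| Control rate | Power against 50%: Wald / LR / Firth | Null error: Wald / LR / Firth |
|---|---|---|
| 5% | 70 / 98 / 97% | 0.0 / 9.5 / 1.1% |
| 3% | 52 / 99 / 99% | 0.0 / 7.5 / 0.3% |
| 2% | 39 / 99.7 / 99% | 0.0 / 5.4 / 0.2% |

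Repeat simulations put the likelihood-ratio error at up to 10.7, 7.8 and 6.6%. Wald was essentially never significant with an empty arm, so its power is capped near 1 − 0.277 = 72%, 1 − 0.467 = 53% and 1 − 0.603 = 40%. Firth gave a finite estimate in every trial.

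**Primary test with and without strata.** At 5% against 50%, power is 98.1% unstratified and 97.8% with Cochran-Mantel-Haenszel (CMH) at 25 per arm, and 98.7% and 98.8% at 28. With assumed control rates by stratum (established/new onset) and log odds ratio 2:

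| Rates | Unstratified power | CMH power | Null error, unstratified / CMH |
|---|---|---|---|
| 5/5 | 64% | 62% | |
| 20/5 | 79% | 81% | |
| 30/5 | 77% | 82% | |
| 40/5 | 71% | 80% | 3.6 / 5.2% |
| 50/5 | 62% | 77% | 2.8 / 4.9% |

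Monte Carlo standard error is about 0.5 point for power and 0.3 for error rates near 5%. With a one-sided test the CMH gain shrinks to about 5.5 points at 40/5 and 11 at 50/5.

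**Baseline C-peptide.** The documents give no SD or prognostic strength. Under an assumed log odds ratio of 1 per SD, adding strata and baseline together to a Firth fit of the planned model raised power from 69 to 76% (20/5) and from 67 to 75% (40/5). The share due to baseline alone was not separated. If baseline predicts nothing, the cost was about 1 point or less.

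**The case against.** The strongest reply is that the primary conclusion is not at risk. The logistic model is an additional analysis, the test of proportions works with an empty arm, and a diverging fit would be noticed in a 56-person pilot. All of that stands. But noticing the divergence does not settle which test to report, and the choice would then be made with the outcomes known.

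Second, the strata loss rests on assumed rates. At 40/5 and 50/5 the overall control rate is (40+5)/2 = 22.5% or (50+5)/2 = 27.5%, well above the figure in 9.7. This also stands. The support in the documents is indirect: 5.4.1 describes a steeper C-peptide decline in the first year after diagnosis, which makes different responder rates in new-onset and established disease plausible but does not quantify them.

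Third, the planned model already adjusts for age and time since diagnosis, from which the strata are cut. This is partly right. Read by likelihood ratio, that model has 78% power at 40/5 and 73% at 50/5, against 80% and 77% for CMH. Its null error there is 6.4 and 6.1%, and it is not the primary test.

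A reader might infer that the two problems compound. They do not: an empty arm needs very low response, and the strata loss needs high response in established disease. At 40/5 an empty arm occurs in about 0.1% of trials.

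**Conclusion.** The point holds as an improvement to the analysis that should be made. It does not threaten the primary result at the plan's own rates.

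- **Strata.** Nothing is lost at 5% against 50%. About 9 to 15 points of power are lost if stratum rates are as far apart as 40/5 or 50/5, at log odds ratio 2 and two-sided 0.05, all assumed. CMH gains about 2 points at 20/5 and loses up to about 2 if strata are alike.
- **Adjusted model.** This part needs no stratum assumption. At the rates in 9.7, maximum likelihood fails in roughly a quarter of trials or more, and the two common readings err in opposite directions.
- **Baseline C-peptide.** Prespecifying it is sound, but the size of the gain is unknown from the documents.

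Three stronger readings are not supported. Ignoring the strata does not inflate false positives; it lowers the error rate. A doubled likelihood-ratio error applies only at the 5% ceiling and fades towards nominal at 2%. The supportive mixed model in 9.4.3 is not affected by this point.

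**What to change.** In 9.4.2:

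(a) Make the primary test an asymptotic Cochran-Mantel-Haenszel test over the four randomisation strata, without continuity correction. Report it with a Mantel-Haenszel stratum-weighted risk difference and 95% interval, which also serves the intention in 9.5.3. State alpha and sidedness.

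(b) Fit the adjusted logistic model by Firth-penalised likelihood, with a penalised profile-likelihood test and interval. Covariates are arm, the two stratum factors and prespecified baseline 90-minute C-peptide. Say explicitly whether continuous age and time since diagnosis are kept or are replaced by the stratum factors. The Firth figures tabulated above are for replacement.

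In 9.4.4, state that baseline C-peptide is in this model whatever the observed imbalance.

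The cost is wording. The objective, endpoint, hypothesis and sample size are unchanged, and every variable is already collected. CMH gives up to about 2 points of power if strata are alike. Firth is conservative at very low rates: null error is about 1% at a 5% rate (2.1% for the unstratified test) and 0.2 to 0.3% at 2 to 3%. Its shrinkage is small, with a mean treatment log odds ratio of 2.90 against a true 2.94 at 5% against 50%. The change should be made before one-year outcomes are examined.
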